## REASEARH SCHEME

## 1. INTRODUCTION

### 1.1 Context:

Increase in intraabdominal pressure (IAP) has been demonstrated to correlate with consequential hemodynamic effects. Several studies have been carried out mostly in experimental settings to define the underlying mechanisms that regulate the pathophysiology following an increase in IAP. In the last years this topic has become concerning because of the wide spread of laparoscopy, that is namely an iatrogenic acute increase in IAP.

Despite most consequences affecting cardiovascular, renal and pulmonary systems could be fairly explained by mechanical/compression insults following increased IAP, there is still lack of knowledge about the neurohormonal responses involved. Many authors have demonstrated the correlation between abdominal and intracranial pressure, which might explain the basis for neurohormonal regulations. There are two mechanisms postulated that could explain these phenomena. An early mechanical stage is explained by compression of the inferior vena cava from a cranial displacement of the diaphragm caused by the insufflation of pneumoperitoneum, which reduces the venous drainage from the lumbar plexus and central nervous system, thereby increasing the pressure in the cerebrospinal fluid. A late arterial mechanism is related to CO2 diffusion through the peritoneal membrane, which results in an increase in PaCO2 and a reflex vasodilation that leads to an increase in intracranial pressure (ICP), following the Monroe-Kellie hypothesis.

The effects of an elevated ICP on renal hemodynamics have been studied under experimental and clinical setting, though not fully understood. Decreased cardiac output and increased vascular and renal resistance were proposed as mechanisms underlying the sudden impairment in renal function following an increased intraabdominal pressure, although correcting the cardiac output did not restore a

normal renal function. Also, placing ureteral stents to counteract high pressure compression on ureters, did not restore a normal urine output either.

Catecholamines and vasopressin release has been proposed to have an important role in this mechanism. About this topic studies have been carried out with the aim of identifying significant antidiuretic hormone changes during laparoscopy and position changes.

Furthermore, several studies have validated the use of optic nerve ultra sound as a non-invasive, accurate, safe, reproducible and cost-effective tool in assessing intracranial pressure (ICP), reducing potentially harming consequences of invasive transcranial measurements.

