## **2. OBJECTIVES**

In a standard operative setting as for sleeve gastrectomy, endotracheal ventilation is routinely administered to patients under general anesthesia. Positive expiratory end-pressure (PEEP) effect on increasing IAP is controversial, still its effect on increasing intracranial pressure (ICP) is widely accepted.

The aim of this study is to investigate any direct correlation between increased intrathoracic pressure, intraabdominal pressure and intracranial pressure, following a controlled elevation in intraabdominal pressure and intrathoracic pressure (PEEP). The second end-point is to investigate any correlation between elevated intracranial pressure and vasopressin release, urine output and urine and serum osmolality by measuring their values at different time-points.

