#### **3.3 Study Interventions and Measures:**

Patients selected and consented for elective surgery will undergo standard of care and additional measurements during and after surgery. These measurements involve minimal risk as the probability and magnitude of physical or psychological harm anticipated in the research are not greater in and of themselves than those ordinarily encountered in daily life, or in routine medical, dental, or psychological examinations. In order to support our pathophysiological hypothesis, we identified 4 different conditions in which the measurements should be done:

- A) Baseline
- B) Patient under general anesthesia, 10-15 minutes after insufflation of pneumoperitoneum at 15mmHg, PEEP at 5cmH2O or lowest setting
- C) 10-15 minutes after stabilization of PEEP at 10cmH2O, pneumoperitoneum still at 15 mmHg
- D) 10-15 minutes after desufflation of pneumoperitoneum and basal mechanical ventilation

Measurements include:

4

V 4 , 2018 01/16/2019 NCT Number: NCT03707054

---

-Intraabdominal pressure IAP: assessed via laparoscopic insufflator, set at 15 mmHg as a standard value for all laparoscopic procedures

-Intrathoracic pressure: indirectly measured by variability of peak expiratory pressures

-Urine collection: Urine output will be measured every shift by the nursing staff from the beginning of surgery to post-operative day 1. The use of Foley catheters during these laparoscopic procedures is dependent on the surgeon's judgment based on patient's co-morbidities. However, in order to participate in this study a Foley catheter needs to be inserted, so the patient will receive a Foley catheter. It will be removed Post-operative day 1.

-Urine osmolality prior to surgery and 8-12 hours post-surgery

-Serum/plasma collection: blood draws to evaluate specific values of

-Plasma Vasopressin (ADH)

-Serum osmolality

-Mean arterial pressure: noninvasive standard anesthesia monitoring

-Pulmonary expiratory end-pressure (PEEP): anesthesiologists routinely adapt PEEP in order to maintain an optimal ventilation, especially in obese patients and during laparoscopy

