#### **Expected results:**

- At higher IAPs (time-points B and C), an increase in vasopressin serum levels, a decrease in urine output and renal function with increased urine osmolality are expected. A significant increase in ONSD is also expected.
- At IAP normalization (time-points A and D), a decrease in vasopressin serum levels and restoration of renal function and urine osmolality are expected.

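### CO2 absorption, which the protocol names as a late route to raised intracranial pressure, is recorded at no time-point, so it cannot be separated from PEEP between B and C or ruled out as carry-over at D

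*Combined protocol and SAP*

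**What the plan says.** Section 1.1 sets out two mechanisms linking pneumoperitoneum to intracranial pressure (ICP). The first is mechanical: "An early mechanical stage is explained by compression of the inferior vena cava from a cranial displacement of the diaphragm". The second, which the protocol labels late, starts with CO2 "diffusion through the peritoneal membrane, which results in an increase in PaCO"2 and continues with "a reflex vasodilation that leads to an increase in intracranial pressure (ICP), following the Monroe-Kellie hypothesis".

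The aim in Section 2 is to "investigate any direct correlation between increased intrathoracic pressure, intraabdominal pressure and intracranial pressure". Its second end-point relates raised ICP to vasopressin. Section 3.4 goes further and asks which of pneumoperitoneum and PEEP accounts for more of the ICP rise, and how much each contributes.

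Section 3.3 fixes the readings. A is baseline. B is "10-15 minutes after insufflation of pneumoperitoneum at 15mmHg" with PEEP at 5 cmH2O or the lowest setting. C is "10-15 minutes after stabilization of PEEP at 10cmH"2O with the abdomen still at 15 mmHg. D is "10-15 minutes after desufflation of pneumoperitoneum and basal mechanical ventilation". The variables listed are intraabdominal pressure (IAP), intrathoracic pressure, urine output, urine osmolality, vasopressin, serum osmolality, mean arterial pressure, PEEP and optic nerve sheath diameter (ONSD).

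No arterial or end-tidal CO2 is listed, and no CO2 target for ventilation is stated. The limitations after Section 3.4 do not mention CO2. Section 5 specifies repeated measures ANOVA and paired t-tests for vasopressin, with no covariate. Section 7.2 takes vital signs and basic laboratory values from the health record, but names no CO2 value and ties nothing to A-D.

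**The concern.** The protocol identifies a cause of raised ICP that is not itself pressure, then plans no data on it. That would matter less if the design separated the two routes in some other way, but it does not. There is one IAP level, no randomised order of conditions and no comparison arm, and the gas and the pressure start and stop together.

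What is at stake is the mechanistic conclusion. If ONSD widens from B to C, the Section 3.4 apportionment would put the whole step down to PEEP, although the patient has also been longer under CO2. If ONSD or vasopressin has not come down by D, nobody could tell whether the response outlasts the pressure or whether CO2 was still raised. Because Section 2 links ICP to vasopressin, the ambiguity can pass from ONSD into the second end-point. Values not captured at the time may not be recoverable in a form matched to each image and blood draw.

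**Working it through.** No figure in the plan bears directly on this point, so the check sets the conditions side by side and asks what changes between them.

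**Inputs (Section 3.3).** Gas exposure at C assumes that C follows B as listed and ignores the time taken to stabilise PEEP:

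- lower end: 10 + 10 = 20 minutes
- upper end: 15 + 15 = 30 minutes

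| Reading | Insufflation pressure | PEEP | Time under gas |
|---|---|---|---|
| A | none | not stated | 0 min |
| B | 15 mmHg | 5 cmH2O or lowest | 10-15 min |
| C | 15 mmHg | 10 cmH2O | at least about 20-30 min |
| D | none | basal ventilation | gas released 10-15 min earlier; total exposure not stated, but no shorter than at C |

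**What each contrast changes.**

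- A to B: pressure and CO2 exposure begin together, along with anaesthesia if A is taken before induction. The sum is the effect of pneumoperitoneum as a whole.
- B to C: insufflation pressure is constant, while PEEP and time under gas both increase.
- C to D: insufflation pressure is removed, ventilation returns to basal, and CO2 may be partly or fully cleared. The documents give no clearance time.

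**Consequence for the apportionment.** Assume additive effects. Let P be the true PEEP effect on ONSD from B to C, s the change in ONSD per unit of arterial CO2, and d the change in CO2 from B to C.

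- Observed step from B to C = P + s × d.
- Let T be the total change from A to C. The share credited to PEEP is (P + s × d)/T, and its true share is P/T.
- Error in the PEEP share = (s × d)/T.

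On the protocol's own mechanism s is positive, so a rise in CO2 (d > 0) overstates PEEP and understates pneumoperitoneum by the same amount. If ventilation held CO2 level, d = 0 and there is no error. If CO2 fell, the error reverses. The documents give neither s nor d, so neither the size nor the actual direction can be computed. With no CO2 value recorded, d would stay unknown after the trial as well.

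**Consequence at D.** By the same notation, the ONSD difference between D and A contains s times the CO2 difference between D and A. That term is zero only if CO2 is back at its value at A, which the plan has no way to show.

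**The case against.** Several stronger readings are tempting, and the documents do not support them.

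- *A reader might infer that no ONSD change at B, C or D can be attributed to pressure.* That goes too far. Section 1.1 calls the mechanical route early and the CO2 route late, so at 10-15 minutes B is probably the least affected reading taken under gas. CO2 is also part of what pneumoperitoneum does: from A to B it is a mediator, not an outside confounder. Section 3.4 treats pneumoperitoneum as one side of its comparison, and the change from A to B can still be attributed to it as a whole. The word direct in the objectives may mean no more than positive.
- *A reader might infer that CO2 load rises from A to C by design.* Only time under gas does. Arterial CO2 also depends on ventilation, on which the documents state no CO2 target. A rise at C and a residue at D are possibilities, not results.
- *A reader might infer that a raised ONSD at D would be counted against the IAP link.* The statement on reversal begins "At IAP normalization (time-points A and D), a decrease in vasopressin serum levels" and goes on to renal function and urine osmolality. It does not name ONSD, and Section 5 specifies no ONSD test. Carry-over concerns vasopressin through ICP, and ONSD by implication.
- *It is also tempting to require that a pressure effect survive adjustment for CO2 before it is claimed.* That would condition on a post-exposure mediator. Since gas and pressure start and stop together, adjustment would rest on differences between patients in CO2 change, read through a proxy. Neither a null nor a persisting adjusted contrast would be decisive.

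End-tidal CO2 may well be displayed in routine anaesthesia, but the plan neither collects nor uses it. So the omission stands, and so do its effects on B to C and on D.

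**Conclusion.** The concern holds in a limited form. The plan cannot separate the pressure component of an ONSD or vasopressin change from CO2. This matters chiefly for the B-to-C step in the Section 3.4 apportionment and secondarily for the interpretation of D. It does not invalidate the A-to-B contrast as an effect of pneumoperitoneum as a whole (subject to whether A precedes anaesthesia), and it leaves the vasopressin sample size calculation untouched.

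The gap in measurement is certain from the text. The bias is not: its size cannot be derived, and it would be nil if CO2 stayed level across the readings. The conclusion assumes that C follows B as listed and that the two-route account in Section 1.1 is correct. This is a cheap improvement that helps the trial answer its own mechanistic question. It is not a reason to doubt that the planned comparisons can be run.

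**What to change.** 1. Add end-tidal CO2 to the Section 3.3 list, read from the anaesthesia monitor at each ONSD image and blood draw at A, B, C and D. At A this applies only where the patient is already ventilated. Section 3.3 states general anaesthesia explicitly only at B, while its ONSD paragraph and the Appendix describe imaging under anaesthesia, so the status of A should be settled first.
2. In Section 5, report the change in end-tidal CO2 beside every ONSD and vasopressin contrast. Add CO2-adjusted B-to-C and C-to-D contrasts as a sensitivity analysis only, with no rule making a pressure claim depend on them.
3. State the attribution in advance: A to B belongs to pneumoperitoneum as a whole (pressure plus CO2), and B to C is not attributed to PEEP alone if CO2 also rose.
4. Add CO2 to the limitations after Section 3.4, including possible carry-over at D.

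The cost is a few monitor values to transcribe per patient, with no added procedure. The adjusted contrasts will be less precise, and end-tidal CO2 is an imperfect proxy for arterial CO2. No change to ventilation is proposed.

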## **2. OBJECTIVES**

In a standard operative setting as for sleeve gastrectomy, endotracheal ventilation is routinely administered to patients under general anesthesia. Positive expiratory end-pressure (PEEP) effect on increasing IAP is controversial, still its effect on increasing intracranial pressure (ICP) is widely accepted.

The aim of this study is to investigate any direct correlation between increased intrathoracic pressure, intraabdominal pressure and intracranial pressure, following a controlled elevation in intraabdominal pressure and intrathoracic pressure (PEEP). The second end-point is to investigate any correlation between elevated intracranial pressure and vasopressin release, urine output and urine and serum osmolality by measuring their values at different time-points.

### **3. STUDY DESIGN**

#### **3.1 General design:**

This study is a prospective study involving patients selected for elective surgery. Patients undergoing bariatric surgery will be enrolled in this study and have several parameters checked as explained below.

#### **3.2 Setting/Participants:**

The study will take place in Cleveland Clinic, Florida in a standard operative setting. An estimated number of patients, based on statistical power analysis, undergoing a Sleeve Gastrectomy will be enrolled to participate in this study.

#### **3.3 Study Interventions and Measures:**

Patients selected and consented for elective surgery will undergo standard of care and additional measurements during and after surgery. These measurements involve minimal risk as the probability and magnitude of physical or psychological harm anticipated in the research are not greater in and of themselves than those ordinarily encountered in daily life, or in routine medical, dental, or psychological examinations. In order to support our pathophysiological hypothesis, we identified 4 different conditions in which the measurements should be done:

- A) Baseline
- B) Patient under general anesthesia, 10-15 minutes after insufflation of pneumoperitoneum at 15mmHg, PEEP at 5cmH2O or lowest setting
- C) 10-15 minutes after stabilization of PEEP at 10cmH2O, pneumoperitoneum still at 15 mmHg
- D) 10-15 minutes after desufflation of pneumoperitoneum and basal mechanical ventilation

Measurements include:

4

V 4 , 2018 01/16/2019 NCT Number: NCT03707054

---

-Intraabdominal pressure IAP: assessed via laparoscopic insufflator, set at 15 mmHg as a standard value for all laparoscopic procedures

-Intrathoracic pressure: indirectly measured by variability of peak expiratory pressures

-Urine collection: Urine output will be measured every shift by the nursing staff from the beginning of surgery to post-operative day 1. The use of Foley catheters during these laparoscopic procedures is dependent on the surgeon's judgment based on patient's co-morbidities. However, in order to participate in this study a Foley catheter needs to be inserted, so the patient will receive a Foley catheter. It will be removed Post-operative day 1.

-Urine osmolality prior to surgery and 8-12 hours post-surgery

-Serum/plasma collection: blood draws to evaluate specific values of

-Plasma Vasopressin (ADH)

-Serum osmolality

-Mean arterial pressure: noninvasive standard anesthesia monitoring

-Pulmonary expiratory end-pressure (PEEP): anesthesiologists routinely adapt PEEP in order to maintain an optimal ventilation, especially in obese patients and during laparoscopy

-Optic nerve sheath diameter (ONSD): B scan with a 7.5-MHz linear ultrasound probe to measure the diameter of the optic nerve sheath 3 mm behind the globe is going to be used. [name], a trained ultrasonographer, under the supervision of an anesthesiologist will take the non-invasive sonographic picture by gliding the probe over the eyelid while the participants are under anesthesia. The ONSD will be measured from the captured picture. Study personnel will record the interaction on the patient's chart and include the measurement in the database.

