### 3.4 Primary study endpoint

- Find a direct and significant correlation between increased IAP level (iatrogenic induced and controlled), ICP, ONSD, vasopressin release and urine output
- Two different pathophysiological mechanisms could potentially elicit an increase in ICP (pneumoperitoneum and PEEP), so that the most accounting mechanism may be investigated and in what proportion

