## **11. APPENDIX**

### **Optice Nerve Ultrasound**

In the operating room, patients are placed in a supine position and intubated, with both eyes protected by patches. Using an ultrasound with a 12-MHz transducer (General Electric Venue 40, USA), the diameter of the ONS is measured at a standard level of 3 mm from its origin in a single eye. The ultrasound machine is kept in the anesthesia work room and available upon request to the anesthesia technician. Before and after each use the probe is cleaned with alcohol pads. A specific ultrasound probe cover is utilized during contact with the patient's eye lid.

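### ONSD, the only listed measure of ICP, has conflicting transducer specifications, and the plan does not fix the eye, probe and site across A to D or mask the reading to time-point.

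*Combined protocol and SAP*

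**What the plan says.** Section 3.3 (Study Interventions and Measures) calls for a "B scan with a 7.5-MHz linear ultrasound probe to measure the diameter of the optic nerve sheath 3 mm behind the globe". On who does it, the text says that "a trained ultrasonographer, under the supervision of an anesthesiologist will take the non-invasive sonographic picture" with the participant under anesthesia. It then says: "The ONSD will be measured from the captured picture". The following sentence has study personnel enter the value in the database. It does not say who places the measurement or what that person knows.

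Section 11 (Appendix, on optic nerve ultrasound) describes the same measurement differently: "Using an ultrasound with a 12-MHz transducer", on one named machine model, where "the diameter of the ONS is measured at a standard level of 3 mm from its origin in a single eye".

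The measures listed in Section 3.3 include no other assessment of ICP, and Section 1.1 presents optic nerve ultrasound as the non-invasive way to assess it. The first item of Section 3.4 (Primary study endpoint) is: "Find a direct and significant correlation between increased IAP level (iatrogenic induced and controlled), ICP, ONSD, vasopressin release and urine output". The second item asks how much of any ICP rise is due to pneumoperitoneum and how much to PEEP. The expected results that follow predict a significant ONSD increase under raised intraabdominal pressure, at B and C.

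**The concern.** Two current descriptions of one measurement name different equipment, and neither is complete. A team working from Section 3.3 and a team working from the appendix could produce ONSD values that are not interchangeable.

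This matters because every statement the trial makes about ICP goes through ONSD. Attribution to pneumoperitoneum or PEEP rests on within-patient contrasts (B minus A, C minus B), and the correlation aim also uses ONSD. The direction of the result is announced in advance and the diameter is read from an image. Unless the reading is masked, the reader's expectation can enter the value.

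**Working it through.** **1. The two descriptions side by side**

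| Item | Section 3.3 | Section 11, Appendix |
|---|---|---|
| Transducer | 7.5 MHz, linear | 12 MHz |
| Level | 3 mm behind the globe | 3 mm from an origin that is not defined |
| Eye | not stated | one eye, side not stated |
| Same eye, probe and level at A to D | not required | not required |
| Number of readings | not stated | not stated |
| Who reads, and masking | not stated | not stated |

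The transducer row is a contradiction. The level row is a difference in wording that may or may not be a difference in site. The remaining rows are gaps.

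**2. How each gap could act**

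Write a patient's reading at condition j as true value + offset(j) + reader shift(j) + random error(j), where the offset comes from probe, level and eye. Then

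B − A = true change + [offset(B) − offset(A)] + [shift(B) − shift(A)] + [error(B) − error(A)].

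- If the offset is constant within the patient, the second term is zero.
- If probe, level or eye changes between time-points, the second term goes straight into the measured change.
- If offsets are constant within patients but differ between them, changes are protected, but a correlation of ONSD levels across patients picks up noise.
- A reader shift linked to the condition does not cancel. A shift of the same size at B and C with none at A would inflate B − A and leave C − B untouched, which would tilt the attribution towards pneumoperitoneum.

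**3. The plan's own figure**

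Section 5 sizes the trial on vasopressin: coefficient of variation 0.455, alpha 0.0083 per comparison, 80% power, 25% increase, N = 57. The log-scale variance is ln(1 + 0.455²) = 0.188 (SD 0.434). The documents give no within-patient correlation. Assuming 0.4 on the original scale, the SD of the log difference is √{2[0.188 − ln(1 + 0.4 × 0.455²)]} = 0.466. A two-sided paired t-test for ln(1.25) then gives N = 57 with power 0.806, and the same assumption reproduces all six rows of Table 1. ONSD does not enter this calculation, so nothing here changes N.

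**4. Illustrations only**

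The documents give no ONSD standard deviation, reliability or expected change. The inputs below are assumptions and show direction, not an estimate for this trial.

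*Noise in a correlation.* Assume N = 57, one value per patient, two-sided alpha 0.05 and a true correlation of 0.40. Observed correlation = 0.40 × √reliability. Power ≈ Φ(√54 × atanh(observed correlation) − 1.96). For example, reliability 0.7 gives 0.40 × 0.837 = 0.335 and Φ(7.348 × 0.348 − 1.96) = 0.725.

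| ONSD reliability | 1.0 | 0.9 | 0.8 | 0.7 | 0.6 | 0.5 |
|---|---|---|---|---|---|---|
| Observed correlation | 0.40 | 0.38 | 0.36 | 0.34 | 0.31 | 0.28 |
| Power | 88% | 84% | 79% | 73% | 65% | 57% |

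*Reader shift.* Assume no true ONSD change, a paired t-test at two-sided 0.0083 (borrowed from the vasopressin plan) and N = 57. A shift of b standard deviations of the paired difference gives noncentrality b√57 = 7.55b.

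| Shift b | 0 | 0.1 | 0.2 | 0.3 |
|---|---|---|---|---|
| Noncentrality | 0 | 0.755 | 1.51 | 2.27 |
| False-positive rate | 0.83% | 2.9% | 12% | 33% |

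The noncentrality grows with √N, so a larger sample makes a false finding from a fixed shift more likely.

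**The case against.** The strongest reply is that nothing here shows actual harm. One trained ultrasonographer takes the pictures and the appendix names one machine model, so in practice the method may well be constant within a patient, and a constant offset cancels in paired differences. That stands: the 7.5-MHz versus 12-MHz conflict is not in itself within-patient error. What remains is that no text requires constancy, and that variation between patients would still affect correlations.

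Three stronger readings are tempting, and the documents do not support them.

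- *That the reader knows the time-point.* The documents are silent. The person scanning in the operating room probably knows the condition, but the diameter is taken from a captured picture and the reader's identity and knowledge are not given. Expectation bias is a risk that is not excluded; it is not a stated feature of the plan.
- *That two different anatomical sites are specified.* Both sections say 3 mm. The appendix wording, "is measured at a standard level of 3 mm from its origin in a single eye", may mean the same place as behind the globe. The defect is an undefined term.
- *That both eyes ought to be averaged.* One eye is a stated choice in the appendix. If reading error were 25% to 50% of single-eye within-patient variance and independent between eyes (both assumed), averaging would cut that variance by half the fraction, 12.5% to 25%. That is the gain from a second eye. It does not measure the harm from the gaps above, and it is no reason to overturn the choice.

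**Conclusion.** The point holds as a specification conflict plus an incomplete measurement procedure for a variable in the primary endpoint. The transducer contradiction is certain from the text. So is the absence of any rule on which eye is used, on constancy of eye, probe and level across A to D, and on masking.

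The consequences are conditional: error in the change if the method varies within a patient, noise in correlations if it varies between patients, and possible bias towards the declared expectation if the reader knows the condition. Their size cannot be computed from the documents, and the tabulated figures rest wholly on assumed reliabilities and shifts. Masking is the most important of the gaps, because neither pairing nor sample size protects against a shift linked to the condition. The plan should be changed on this point because the remedy is cheap. The sample size is not called into question by it.

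**What to change.** 1. Reconcile Section 3.3 and the appendix on one transducer and one measurement level, with the anatomical reference defined. The choice is the investigators'; the requirement is that both sections say the same.
2. State which eye is used, and require the same eye, probe and level at A, B, C and D in each patient.
3. State who measures the images. Have the images that are already being captured measured after surgery, in random order, with patient and time-point labels hidden, including any annotation on the picture. State how many readings are taken.

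The cost is protocol wording, relabelling of stored images and a short delay before ONSD values are available. It needs no extra staff or procedure, and N = 57 stays as it is because it rests on vasopressin.
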